### 6.1.5 Device Specific Considerations

This study will employ an external device to deliver the radiation therapy.

- Device brand: Varian
- Device model: TrueBeam® linear accelerator v2.7 or later
- Device accessories employed in this study: MLC, OBI, EPID

## 6.2 Study Agent Accountability Procedures

Quality assurance for the linear accelerator, OBI, EPID and MLC system will be routinely assessed as part of the current department policy and procedures (P&P) in accordance with the American Association of Physicist in Medicine (AAPM) task group 142.

All upper body plans will include volumetric modulated fields and will undergo patient specific QA (PSQA) prior to treatment using the electronic portal imaging device (EPID). The recorded data will be analyzed using two systems: SNC PerFraction (Fraction 0 module) and Varian Portal Dosimetry. Each field will be required to pass, with a passing rate of at least  $\geq 90\%$  using a gamma criterion of 5% at 3mm using both tools, with a preferred passing rate of  $\geq 95\%$  using a gamma criterion of 3% at 3mm.

#### CONFIDENTIAL

This material is the property of the NYU School of Medicine and Langone Medical Center. Do not disclose or use except as authorized in writing by the study sponsor

During treatment, in vivo transit dosimetry for all VMAT fields will be acquired using Varian EPID and evaluated using SNC PerFraction (Fraction N) for dose tracking.

A backup plan using a conventional treatment at extended distance will be in place in case the linac scheduled to deliver the radiation as outlined in this document becomes unavailable for technical issues that require extended maintenance incompatible with the preset treatment schedule. Backup delivery will only be considered if the linac or imaging capabilities are down. Unavailability of transit dosimetry will not prevent treatment.

### 6.2.1 Administration of Procedural Intervention

Radiation therapy will be delivered by the RTTs at the department of Radiation Oncology with a qualified medical physicist (QMP) present. Participants will be positioned head first supine on the linac couch using the immobilization devices prepared at time of simulation. Participants will be triangulated using tattoos or radiopaque markers placed at simulation. Imaging will be acquired for patient positioning verification with a minimum of MV-kV orthogonal in the pelvic and head region and CBCT in the thoracic region. Optimal imaging shifts will be calculated based on all imaging and shifts will be applied when deemed necessary for accurate patient delivery and according with our tolerance tables. Imaging will be approved by physician to the first treatment and prior to subsequent fraction for all other fractions. Subjects will be treated sequentially for four regions: head, thorax, abdomen and pelvis. Subjects will then be repositioned feet first. Imaging will be acquired as per policy for positioning verification and shifts applied as needed. After positioning and imaging, treatment will be delivered to the lower body.

Subjects will be treated twice a day (BID) over four consecutive days with an interfraction break of at least 6 hours from the end of the previous treatment to the start of the following treatment. Approximate duration of the treatment is expected to range from 1 to 1.5 hours depending on participant setup, need for re-positioning, imaging, shifts, and treatment delivery time. However, it might extend past 1.5 hours for some cases.

### 6.2.2 Procedures for Training of Clinicians on Procedural Intervention

The physics section of the department provided training to therapists in all aspects of treatment simulation and treatment delivery in the form of dry runs and training sections. Treatment planning, treatment simulation and treatment delivery will be provided in accordance with written policies and procedures established in our department for this protocol.

### 6.2.3 Assessment of Clinician and/or Participant Compliance with Study Procedural Intervention

Compliance with procedural intervention will be assessed according to internal policy and procedure. This will include complete delivery of dose in the number of fractions and intervals described in the study, presence of all required documentation uploaded to ARIA and required approval of imaging by physician.

## 7 Study Procedures and Schedule

Activity	Consult visit a	Simulation Visit	On treatment visit while receiving radiation	Follow up b >100 days after transplant	1 year follow up c
----------	----------------------------	------------------	--	---	-------------------------------

CONFIDENTIAL

This material is the property of the NYU School of Medicine and Langone Medical Center. Do not disclose or use except as authorized in writing by the study sponsor

			(routine practice)		
Study team procedures					
Consent	X				
Medical History	X			X	X
Physical Exam	X		X	X	X
Height	X				
Weight	X				
Vitals signs	X		X	X	X
Laboratory Assessments					
Urine Pregnancy test for premenopausal participants	X	X (if not performed at consult)			
Pulmonary function tests	(pre-transplant)				X
Imaging Assessments					
CT simulation scan		X			
Adverse Events			X	X	X

a If not obtained at Consult visit, an additional visit will be added to obtain Consent/conduct screening

b @ >100 days and <150 days Follow up visit after transplant, ( ± 14 days)

c At one year follow-up following transplant, ( ± 30 days)

## 7.1 Study Procedures/Evaluations

### 7.1.1 Study Specific Procedures

- Consult
- CT-simulation
- TBI treatments
- Follow up

### 7.1.2 Standard of Care Study Procedures

The delivery of TBI as conditioning regimen for ASCT is considered an acceptable standard of care. As such, the novel aspect of this study is the way the TBI will be planned, i.e. with VMAT-based approach.

## 7.2 Laboratory Procedures/Evaluations

### 7.2.1 Clinical Laboratory Evaluations

A urine pregnancy test will be performed in all women of child-bearing potential prior to CT simulation.

Subjects will have daily laboratory evaluations immediately following ASCT as standard of care.

#### CONFIDENTIAL

This material is the property of the NYU School of Medicine and Langone Medical Center. Do not disclose or use except as authorized in writing by the study sponsor

Imaging will be performed as SOC following ASCT including chest x-rays or cross-sectional imaging as clinically indicated.

As the primary endpoint is a dosimetric endpoint, no specific laboratory or clinical imaging is required. All laboratory and clinical examinations ordered as SOC will be considered in determining the etiology of any pulmonary symptoms and whether it meets criteria for the secondary endpoint.

### **7.2.2 Other Assays or Procedures**

Imaging will be performed as SOC following ASCT as clinically indicated. PFTs will be performed one year out.

## **7.3 Study Schedule**

### **7.3.1 Enrollment/Baseline**

The transplant team notifies radiation oncology of patients requiring TBI with a formal consultation request form, which lists the dose of TBI required and the specified dates for TBI and the transplant. Once a TBI consult request is placed, the patient is scheduled for consult and simulation. For any patient for whom the transplant team is requesting full dose ( $\geq 12$  Gy) TBI, the radiation oncology team will broach the prospective subject regarding trial participation at the time of consult.

#### **Enrollment/Baseline Visit (Visit 1, radiation oncology consultation)**

- Obtain informed consent of potential participant verified by signature on study informed consent form.
- Verify inclusion/exclusion criteria.
- Obtain urine pregnancy test.
- Obtain demographic information, medical history, medication history, alcohol and tobacco use history.
- Record vital signs, results of examinations, other assessments.
- Baseline PFTs

### **7.3.2 Intermediate Visits**

#### **CT Simulation**

The simulation may take place on the day of radiation oncology consultation or on a different day. If on a different day, a urine pregnancy test will be obtained within 7 days of simulation for all women of child-bearing potential.

#### **7.3.2.1 Visit 2-5**

TBI treatments will be delivered as per the transplant team, usually BID for 4 days. The most common regimens used will be 150cGy BID x 4 days and 165cGy BID x 4 days.

Need to record conditioning regimen data

#### **Visit 2-5 (Days of TBI)**

- During at least one of the radiation treatments, a radiation oncology attending will see the participant for an on treatment visit (OTV) and assess the participant for any acute side effects.

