kidney dose < 8 Gy), and another patient with previous whole brain irradiation (mean dose <11.7 Gy with central brain area reduced to 6 Gy). Five patients received full dose while two patients received only 8 Gy due to general condition and performance status. The mean follow-up after TBI of all patients was 8 months (2.3 to 15 months). During radiotherapy, all patients suffered from slight to moderate fatigue and pre-existing anemia. Immediately after TBI, all patients suffered from grade 3 mucositis and received analgesic therapy. No modest or severe lung reaction was observed during follow-up. One patient was treated during relapse without obtaining remission after chemotherapy, died of refractory disease 2.3 months after TBI. One additional patient relapsed 8.8 months after treatment (mediastinum and neck nodes) and died after 13.4 months. The other five patients were disease free and without severe toxicities.

Tas et al., treated thirty patients using linac based VMAT TBI. Age ranged from 6 to 63 years old (19 male, 11 female). Prescription was set in such a manner that 90% of the clinical target volume (the whole body) received 12 Gy in six fractions (two fractions of 2Gy per day). Mean doses to total lung and total kidney were restricted to less than 10 Gy and the maximum dose to the lens was restricted to less than 6 Gy. Average total lung mean dose was 9.7 Gy, total kidney mean dose was 9.6 Gy and maximum lens dose was 4.5 Gy. Mean dose was 12.7 Gy (106% of prescription dose). Mean and median follow-up times were 16 and 18 months. TBI induced acute toxicity was low with only grade 1 and 2 morbidity including patchy mucositis in 16, nausea in 12, headache in 11, fatigue in 9, neck pain in 8, xerostomia in 7, loss of appetite in 6 and faint or dull erythema in 4 patients. Grade 3 or more acute radiation toxicity was not observed. All patients were still alive at follow-up, and no leukemia relapse was observed (mean follow-up time of 16 months).

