#### **2.4.3 Known Potential Benefits**

A potential benefit of linac based VMAT TBI, as opposed to our current approach of using opposed laterals to deliver TBI, is that we can minimize the dose to the lungs, without compromising coverage in the thoracic region outside of the lungs. This will have the potential of reducing the risk of idiopathic pneumonia syndrome while maximizing the effectiveness of TBI. We limit the mean dose to the kidneys, which has the potential to prevent renal dysfunction.

Since the initial writing of this protocol, Stanford has published their VMAT TBI experience which includes primarily pediatric patients (23/35 patients <18 years old). Their series includes 35 patients treated with VMAT TBI, 13 with doses of 12Gy or higher as per this protocol. Their dose objectives are similar to ours with a D90% $\geq$ 100% for the PTV body a Dmax $\leq$ 120%, Dmean of lungs  $\leq$ 660cGy. Of note, they also constrict their kidney dose and lens dose for myeloablative regimens. Their toxicity data (unpublished, data courtesy of [name] and [name]) is very favorable with a 4% rate of grade 2 pneumonitis (n=1, present before RT), 4% rate of grade 1 nephrotoxicity (n=1, present before RT), 40% diarrhea (4% grade 3), 56% rate of fatigue (all  $\leq$  grade 2), 76% rate of nausea (4% grade 3), 84% rate of mucositis (36% grade 3), and 16% rate skin toxicity (all  $\leq$  grade 1).

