#### **6.1.1 Dosing and Administration**

Radiation dose will be administered according to the physician's written directive. Treatment will be administered twice a day over four consecutive days with an interfraction daily break of at least 6 hours between the end of the first fraction and the start of the next fraction.

Treatment will be administered by registered radiation therapists (RTTs). Prior to administration, the imaging system will be deployed to acquire kV, MV orthogonal projection radiography image(s) as well as CBCT image(s) to confirm accurate patient positioning. Optimal patient positioning shifts will be calculated and applied as deemed necessary based on acquired imaging. The imaging will be performed prior to the actual first day of treatment for the first patient (films only day). After that subject, we will re-evaluate the need for subsequent films only days. During delivery, the electronic portal imager device will be deployed to record the dose delivered to the participant. This technique, known as transit dosimetry, will be used to evaluate the accuracy of the treatment delivery as mentioned above.

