#### **7.3.2.2 Visit 6**

#### **Visit 6 (>100 days and <150 days post-transplant):**

#### **CONFIDENTIAL**

This material is the property of the NYU School of Medicine and Langone Medical Center. Do not disclose or use except as authorized in writing by the study sponsor

- The subject will be seen in follow-up between 100-150 days post-transplant for assessment of adverse events, with specific attention to non-infectious pneumonia syndrome. All interval thoracic imaging performed will be reviewed along with the interval history.

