#### CONFIDENTIAL

This material is the property of the NYU School of Medicine and Langone Medical Center. Do not disclose or use except as authorized in writing by the study sponsor

The PI will record all reportable events with start dates occurring any time after informed consent is obtained until at least 100 days (for non serious AEs) or up to one year post transplant (for SAEs) after the last day of study participation. . At each study visit, the investigator will inquire about the occurrence of AE/SAEs since the last visit. Events will be followed for outcome information until resolution or stabilization.

All unresolved adverse events should be followed by the investigator until the events are resolved, the subject is lost to follow-up, or the adverse event is otherwise explained. At the last scheduled visit, the investigator should instruct each subject to report any subsequent event(s) that the subject, or the subject's personal physician, believes might reasonably be related to participation in this study. The investigator should notify the study sponsor of any death or adverse event occurring at any time after a subject has discontinued or terminated study participation that may reasonably be related to this study. The sponsor should also be notified if the investigator should become aware of the development of cancer or of a congenital anomaly in a subsequently conceived offspring of a subject that has participated in this study.

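### No graded acute-toxicity assessment is fixed at the end of TBI or in the weeks after it, and section 8.3 leaves unclear which acute toxicities are recorded

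*Combined protocol and SAP*

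**What the plan says.** **During TBI.** Section 6.1.1: "Treatment will be administered twice a day over four consecutive days". Section 7.3.2.1 names 150 cGy and 165 cGy twice daily for four days as the commonest regimens. It labels the TBI days Visits 2 to 5 and states: "During at least one of the radiation treatments, a radiation oncology attending will see the participant for an on treatment visit (OTV"). The attending is to "assess the participant for any acute side effects". The fraction is not specified.

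**After TBI.** Section 7.3.2.2 (Visit 6): "The subject will be seen in follow-up between 100-150 days post-transplant for assessment of adverse events". The footnote to the section 7 schedule table reads ">100 days and <150 days Follow up visit after transplant, ( ± 14 days"). The table marks adverse events in three columns only: the on-treatment visit, the visit after day 100, and one year.

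**General rules.** Section 8.3: "At each study visit, the investigator will inquire about the occurrence of AE/SAEs since the last visit". It also has events come to notice when a participant presents for care or when a monitor reviews the record, and it requires every event to be documented whatever its relationship. Changes in severity are to be documented so that duration at each level can be assessed. Section 8.4.1 requires specific questioning at each contact, immediate recording, and CTCAE version 5.0 grading.

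**The same section 8.3, further on.** Adverse events are described there as unexpected toxicities, with hematologic and gastrointestinal toxicities given as examples of what is expected. The list to be reported and monitored consists of grade 3 or higher non-hematologic toxicity directly related to study drugs, and grade 2 or higher bilirubin.

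**Background rates.** Section 2.2.2, on a seven-patient VMAT series: "Immediately after TBI, all patients suffered from grade 3 mucositis and received analgesic therapy". Section 2.4.3, on another institution's series: "84% rate of mucositis (36% grade 3").

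**The concern.** The protocol summary calls this a study of safety, and section 2.4.1 acknowledges a higher dose rate and possible unknown toxicity. The visit dedicated to acute side effects can fall at any fraction, so the dose already received when it takes place can differ between subjects. One cited series places severe mucositis immediately after TBI, which is the start of the period without a scheduled study visit.

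Two safety rules depend on how often events occur. Section 8.2.3 treats an event as unexpected if, among other things, its frequency is inconsistent with the described risk. Section 9.1.1 has the DSMC look through cumulative toxicities for unexpectedly elevated frequency. If acute events are recorded unevenly, both rules work from a count of unknown completeness.

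**Working it through.** The plan gives no figure for acute toxicity, so there is none to reproduce. Its one design calculation, the 68.9% confidence limit in section 10.1, concerns the dosimetric proportion and does not enter here.

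**1. Dose at the on-treatment visit.** Fractions: 2 per day × 4 days = 8. If the visit is at fraction 1, the share of dose received is at most 1.5/12.0 = 1.65/13.2 = 12.5%. At fraction 8 it is 100%. Any value between complies with section 7.3.2.1. This describes uneven timing; it does not measure under-recording.

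**2. Interval to the next scheduled visit.** Day 100 to 150 by section 7.3.2.2. If the footnote's ±14 days applies to the window edges, 100 − 14 = 86 and 150 + 14 = 164, so day 86 to 164. The time from TBI to transplant comes on top; the documents do not give it.

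**3. What the general rules supply.**

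| Need | Provided? |
|---|---|
| Questioning about events on TBI days | Yes: Visits 2 to 5 are study visits (8.3), and every contact counts (8.4.1) |
| Severity scale | Yes: CTCAE v5.0 |
| Capture between TBI and about day 100 | Partly: on presentation for care, on monitor review, and by look-back at the next visit |
| A graded assessment at the same point for every subject | No |
| A clear rule that expected acute toxicities are recorded | No: section 8.3 points both ways |

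On the narrower wording of section 8.3, nausea and diarrhea, being gastrointestinal, could be left out, as could mucositis if a site counts it with them. Grade 1 and 2 fatigue and skin toxicity fall below the monitored threshold.

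**4. Cited rates of severe acute toxicity.**
- Seven-patient VMAT series (2.2.2): grade 3 mucositis in all, 100%.
- Other institution's series (2.4.3): 36% grade 3 mucositis. It reports 4% as one patient, which implies about 1/0.04 = 25 assessed patients. Only 13 of its 35 patients received 12 Gy or more.
- Ten-patient tomotherapy series (2.2.2): no grade 3 or 4 effects directly related to TBI.
- Thirty-patient VMAT series (2.2.2): no acute radiation toxicity of grade 3 or more.

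The range is 0% to 100%, so no single expected count for this trial follows.

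**5. Illustration only.** Assume that the 36% and 84% mucositis rates carry over to all 35 subjects: 0.36 × 35 = 12.6, about 13, and 0.84 × 35 = 29.4, about 29. With complete capture, the exact two-sided 95% intervals are 21.5% to 55.1% for 13/35 and 66.4% to 93.4% for 29/35. Recorded rate = true rate × capture:

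| Assumed capture | Recorded, if true rate is 36% | Recorded, if true rate is 84% |
|---|---|---|
| 75% | 27% | 63% |
| 50% | 18% | 42% |
| 25% | 9% | 21% |

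The reverse reading matters for the DSMC. A recorded 36% would correspond to a true 0.36/0.75 = 48% at 75% capture, or 0.36/0.50 = 72% at 50%.

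**The case against.** The strongest reply is that adverse-event collection is not confined to the on-treatment visit. The TBI days are themselves study visits at which events must be asked about, and section 8.4.1 extends this to every contact. A subject questioned only at fraction 1 would not have been managed according to the whole protocol. Section 8.3 covers presentation for care, and section 12 adds monthly evaluation and quarterly monitoring. All of this stands. It rules out the inference that the on-treatment visit is the only inquiry during TBI, or that the weeks before day 100 go unrecorded.

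A reader might also infer that subjects who die before the visit after day 100 are never assessed. The documents do not support that: sections 8.4.2 and 8.6 send deaths and life-threatening events to an SAE form within 24 hours, and section 7.3.4 collects adverse events at withdrawal. An SAE form for a death is not, however, a record of the peak grade of each acute toxicity.

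Finally, no objective, endpoint or analysis in sections 3, 4 or 10 compares acute toxicity with published rates, and the cited rates are background. That is correct, and it limits the point to the safety review and to informal comparison. It does not remove it, because the rules in sections 8.2.3 and 9.1.1 turn on frequency.

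**Conclusion.** The point holds as a gap in standardisation. The general rules provide for collection, but no graded acute-toxicity assessment is fixed at a common point, and section 8.3 does not settle whether expected toxicities are recorded. Recording may therefore be incomplete and may differ between subjects.

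It would be tempting to conclude that acute toxicity is under-recorded, or that it cannot be set against the cited series. Neither is supported. The documents give no capture rate, so the percentages under assumed capture show sensitivity and are not estimates. A comparison would be open to undercounting but would not be impossible, and the cited series disagree so widely that it would be loose even with complete data.

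The dosimetric primary endpoint is untouched. So is the IPS endpoint, which Visit 6 addresses directly. This is a low-cost improvement to the safety data, not a threat to the main result.

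**What to change.** Leave the clinical visits as they are, and make four changes to data collection:

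1. Complete a CTCAE v5.0 acute-toxicity CRF (mucositis, nausea, diarrhea, fatigue, skin) for every subject at the last TBI fraction received.
2. At transplant discharge or death, abstract the peak grade of each item from the inpatient chart.
3. Show both in the section 7 schedule table.
4. Reconcile section 8.3 so that it is clear these toxicities are recorded even when expected, and keep the rule for what is recorded separate from the list of what is reported and monitored. A new CRF time point alone would leave that conflict in place.

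The cost is one form while the subject is already in the department and a short chart abstraction, so a little more data entry. No visit or test is added.
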